COVER PAGE

TITLE:

Efficacy and safety of low dose Amisulpride Versus Olanzapine-Fluoxetine Combination in the treatment of Post Schizophrenic Depression: A Randomised Controlled Trial

NCT04876521

DATE: June 1, 2019

STUDY PROTOCOL, STATISTICAL ANALYSIS PLAN & INFORMED CONSENT FORM

STUDY PROTOCOL

FULL TITLE:

Efficacy and safety of low dose Amisulpride Versus Olanzapine-Fluoxetine Combination in the treatment of Post Schizophrenic Depression: A Randomised Controlled Trial

BRIEF TITLE:

Low Dose Amisulpride Vs Olanzapine-Fluoxetine Combination in Post-Schizophrenic Depression (PSD-AOFC)

SCIENTIFIC BACKGROUND:

About one-fourth of patients who have schizophrenia ultimately develop post-schizophrenic depression (PSD) with higher morbidity and mortality risks, including a higher number of suicides (1-2). Studies regarding the pharmacological treatment options for PSD are scarce. Very few clinical trials have been conducted with antipsychotics involving small study samples (3-4). Moreover, antipsychotics are Serotonin-Dopamine Antagonists, an action opposite to that of antidepressants (5), so their exact role in treating PSD needs further exploration. Antidepressants have been used in schizophrenia with depression but have shown little success (6). An antipsychotic along with an antidepressant (like an olanzapine-fluoxetine combination, OFC) is now the commonly practised treatment strategy in PSD. However, there is insufficient evidence in the literature confirming its rationality.

Studies have shown that amisulpride in a lower dose range (50-400 mg/day) has shown antidepressant actions (7). However, amisulpride has never been explored in PSD. Amisulpride monotherapy might have the added advantage of avoiding polypharmacy in these patients.

Also, correlating the clinical findings with changes in serum Brain-Derived Neurotrophic Factor (BDNF), a neuro-biomarker constantly studied in depressive conditions, would help substantiate the results (8). In our present study on PSD, we would like to corroborate the efficacy of the interventions (low-dose amisulpride versus OFC) with the changes in serum levels of BDNF.

NULL HYPOTHESIS:

There is no difference in the change in the Calgary Depression Scale for Schizophrenia (CDSS) scores between the study groups over 8 weeks.

ALTERNATE HYPOTHESIS:

There is a difference in the change in the Calgary Depression Scale for Schizophrenia (CDSS) scores between the study groups over 8 weeks.

AIM:

To compare the efficacy and safety of low dose Amisulpride Versus Olanzapine-Fluoxetine Combination and in patients with Post Schizophrenic Depression.

STUDY OBJECTIVES:**PRIMARY OBJECTIVES:**

1. To evaluate the change in the severity of depression in terms of change in Calgary Depression Scale for Schizophrenia (CDSS) scores in the study groups over 8 weeks

SECONDARY OBJECTIVES:

1. To evaluate the change in symptom severity and improvement in terms of change in Clinical Global Impression (CGI) scores in the study groups over 8 weeks
2. To evaluate the change in serum BDNF levels in the study groups over 8 weeks
3. To determine the correlation (if any) between the changes in CDSS scores, CGI scores and serum BDNF levels
4. To detect adverse drug reactions (if any) and grading their severity

MATERIALS AND METHODS**STUDY SETTING:**

The proposed study will be conducted at the Out-Patient (OP) and the In-Patient (IP) settings of the Department of Psychiatry, All India Institute of Medical Sciences, Bhubaneshwar.

STUDY DESIGN:

The proposed study will be a randomized, rater-blinded, controlled, clinical trial

STUDY PERIOD:

The study will be conducted within the time frame of two years.

STUDY POPULATION:

The proposed study will be conducted on the patients diagnosed with Post Schizophrenic Depression of the catchment area pertaining to AIIMS, Bhubaneswar.

INCLUSION CRITERIA:

All patients coming for treatment at the OPD and IPD of the Department of Psychiatry fulfilling the following are included:

1. Patients with Post Schizophrenic Depression according to ICD10-DCR (International Classification of Diseases 10– Diagnostic Criteria for Research) (9).
2. Aged between 18 to 60 years of either sex
3. Patients with a positive score of less than 29 on the Positive and Negative Syndrome Scale (PANSS) (10)
4. Patients with a score of more than 6 on the Montgomery-Asberg Depression Rating Scale (MADRS) (11)
5. Patients without Extrapyramidal symptoms: a score of less than 3 on the Simpson-Angus Scale (12)
6. With Informed consent from the Legally Authorised Relative

EXCLUSION CRITERIA:

Patients with any one of the following are excluded from the study:

1. Patients with a medical or neurological disorder
2. Patients with a history of substance dependence
3. Patients with high suicidality
4. Patients with a past history of primary depression
5. Patients already on Olanzapine-Fluoxetine combination or Amisulpride

METHODOLOGY:

The proposed study would be an 8-week, randomised, controlled, parallel-group, clinical trial which will be conducted at the Inpatient and Outpatient settings of the Department of Psychiatry, AIIMS, Bhubaneswar. Patients with the diagnosis of Post Schizophrenic Depression according to the ICD 10 (DCR) and meeting all the Inclusion and Exclusion Criteria would be selected for the study. At first, the patients and their family members/ guardians would be explained about the study procedure along with its possible risks and benefits using a Patient Information Sheet (in their local language). After obtaining a written Informed Consent from the Legally Authorised Relative, the patients would be finally recruited for the study.

All recruited patients would be randomized using computer-generated random numbers into two treatment groups with an allocation ratio of 1:1. The sociodemographic and clinical data of the patients would be collected as per the designed sheets. Then at baseline, the CDSS and CGI ratings would be assessed, and the serum BDNF would be tested for each patient. The study would be rater-blinded. The experimental group would receive Amisulpride at a low dosage of 100-300 mg/day and the control group would receive a combination of Olanzapine at 5mg or 10 mg/day and Fluoxetine at 20mg/day.

The two groups would be followed for 8 weeks, at the completion of which all the patients would be reassessed. The follow-up assessment would involve a re-evaluation of the CDSS and the CGI scores and the Serum BDNF levels to see for any change. The data thus collected would be analysed, compared within and in between the study groups and statistical tests would be applied for drawing conclusions.

RANDOMIZATION:

All recruited patients will be randomized by computer-generated random number into two treatment groups with an allocation ratio of 1:1.

BLINDING:

The proposed study will be rater-blinded. The ratings of the CDSS and CGI scales would be done by a psychiatrist who would be blinded to the nature of the intervention provided.

FOLLOW UP:

All patients under the study will be followed for a period of 8 weeks from the start of the intervention. Then, the follow-up assessments will be done by rating the CDSS, and the CGI scales once again in each patient. Serum BDNF levels will be tested again. The data obtained will be compared within each group to find the change before and after the respective interventions. Thereafter, the magnitude of the changes will be compared in-between the groups to find out the efficacy and safety of one treatment over the other. All the results will be statistically tested to understand their significance.

OUTCOME MEASURES:**Primary Outcome Measure:**

1. Calgary Depression Scale for Schizophrenia (CDSS) [Time Frame: 8 weeks]

Calgary Depression Scale for Schizophrenia (CDSS) (13) scores will be used to measure the change in the severity of depressive symptoms in the study groups from baseline over 8 weeks. the total score ranges from 0 - 36. Higher scores represent higher severity of depression.

Secondary Outcome Measures:

1. Clinical Global Impression (CGI) [Time Frame: 8 weeks]

Clinical Global Impression (CGI) scores (14) will be used to measure the change in illness severity, global functioning and improvement in the study groups from baseline over 8 weeks.

- The Clinical Global Impression - Severity scale (CGI-S) is a 7-point scale [minimum: 1 and maximum 7]: Higher scores means higher severity of disease.
- The Clinical Global Impression - Improvement scale (CGI-I) is a 7 point scale [minimum: 1 and maximum 7]: Higher scores means more clinical improvement.

2. Serum BDNF Levels [Time Frame: 8 weeks]

The change in serum BDNF levels in the study groups over 8 weeks.

3. Correlation [Time Frame: 8 week]

Determine the correlation (if any) between the between changes in CDSS scores, CGI scores and serum BDNF levels

4. Adverse Drug Reactions [Time Frame: 8 weeks]
Detect adverse drug reactions (if any) and grading their severity

STATISTICAL ANALYSIS PLAN:

1. The CDSS scores, the CGI scores and the serum levels of BDNF, being continuous variables would be expressed as a mean \pm standard deviation (SD) / standard error of means (SEM)
2. The means would be compared within the group by two-sided paired t-test / Wilcoxon signed rank test
3. The means between the groups would be compared using unpaired t-test / Mann Whitney U test
4. Correlation analysis will be done between the CDSS ratings, the CGI scores and the serum BDNF levels.
5. The missing values would be replaced by the help of multiple imputations for conducting an Intention to Treat (ITT) analysis and the pooled data would be used for further analysis
6. All the statistical analyses would be performed using SPSS 23.0 (IBM, NY USA)
7. For obtaining statistically significant results, P value would be set at < 0.05

SAMPLE SIZE CALCULATION:

A sample size of 26 per group will achieve a power of 80%, to detect a difference of 3 in Calgary Depression Scale for Schizophrenia (CDSS) between the groups with known SD of 3.8 and with a significant level 0.05 using a Two-sided Two-sample T-test. Assuming attrition of 10-15% 30 patients in each group will be recruited.

Sample size calculation was done by PASS software (Version 11)

EXPECTED OUTCOME:

- The role of low dose Amisulpride in the treatment of Post Schizophrenic Depression can be explored for the first time (as no study has been done on it yet)
- Low dose Amisulpride is expected to be more efficacious than Olanzapine-Fluoxetine combinations in PSD. If this comes true, a new treatment strategy in PSD would be obtained.
- Use of Amisulpride in PSD would have the following advantages:
 1. Polypharmacy in PSD patients can be avoided
 2. Overall reduction in the medical expenditure of the patients
 3. Duration of treatment would not be an issue as in the case of treatments with antidepressants
 4. In advent of positive symptoms simply hiking the Amisulpride doses to higher dose range can treat the patients, without switching to any other antipsychotic.
 5. Lesser risk of side-effects in the patients, as Amisulpride is a relatively safer drug among other antipsychotics

ETHICAL ISSUES:

1. All works under the proposed study would begin only after obtaining approval from the Institutional Ethics Committee, AIIMS Bhubaneswar
2. All the patients and their family members/ guardians would be adequately explained, in the language they understand, about the study procedure and the possible risks and benefits associated with it. Only those patients with a written Informed Consent from the Legally Authorised Relative would be enrolled for the study.
3. Strict confidentiality would be maintained about the identity, sensitive information and personal details of the patients obtained during the course of the study.
4. Any patient can willfully withdraw his/ her participation at any point during the course of the study.

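### The plan applies one baseline, change-score and paired-test scheme to both CGI scales without exempting CGI-I, so the within-arm CGI-I test rests partly on an undefined pre-treatment entry, or cannot be run

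*Combined protocol and SAP*

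**What the plan says.** The Outcome Measures section (secondary outcome 1) describes two scales, each scored 1 to 7. On CGI-S a higher score means more severe illness. On CGI-I, "Higher scores means more clinical improvement". Nothing more is said about CGI-I: no score is named as no change, and no rating time is given for it separately.

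Elsewhere the two scales are not told apart:

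- Secondary objective 1 evaluates "change in symptom severity and improvement in terms of change in Clinical Global Impression (CGI) scores".
- Methodology, before treatment: "Then at baseline, the CDSS and CGI ratings would be assessed". At the end of follow-up there is a "re-evaluation of the CDSS and the CGI scores and the Serum BDNF levels to see for any change".
- Follow Up has the assessor "rating the CDSS, and the CGI scales once again in each patient", and then: "The data obtained will be compared within each group to find the change before and after the respective interventions".
- Secondary outcome 1 uses CGI to measure "change in illness severity, global functioning and improvement in the study groups from baseline over 8 weeks".
- Statistical Analysis Plan item 1 groups "The CDSS scores, the CGI scores and the serum levels of BDNF, being continuous variables". Item 2 gives the within-group test (paired t or Wilcoxon signed rank), item 3 the between-group test (unpaired t or Mann-Whitney U), and item 4 a correlation analysis that again refers only to CGI scores.

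No sentence exempts CGI-I from any of these steps.

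**The concern.** CGI-S describes a state, so subtracting a baseline value from a week-8 value gives a meaningful change. CGI-I, on the protocol's own description, is already a rating of improvement. Before treatment there is no improvement on study medication to rate, so any baseline value is a convention, and the protocol does not say which one. The paired test asks whether the mean week-8 rating differs from that entry. It answers the intended question, whether patients improved, only if the entry is the no-change score.

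At stake is the within-arm CGI-I result that the plan promises for each group. Two analysts following the text could enter different baseline values, or none, and report different conclusions from the same week-8 ratings.

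**Working it through.** **The plan's own figure.** The plan gives no CGI-I value. Its one design calculation concerns CDSS: difference 3, SD 3.8, two-sided 0.05, 80% power. The normal approximation gives n = 2 × (1.960 + 0.842)² × 3.8² / 3² = 25.2, rounded up to 26 per group, as stated. CGI does not enter it, so this point leaves the sample size untouched.

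**What each reading of the text leads to.**

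1. CGI-I is rated at both times and the baseline entry is the no-change score. The paired test is then an ordinary one-sample test of improvement, and is valid.
2. CGI-I is rated at both times and the baseline entry is some other constant. The test is against the wrong reference value.
3. CGI-I is rated at baseline as improvement over some earlier, unspecified period. The difference is then between two improvement ratings with different reference points, and has no clear meaning.
4. CGI-I is rated at week 8 only. Item 2 of the Statistical Analysis Plan cannot be carried out for it.

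**Size, by illustration.** Inputs: n = 30 per arm (Sample Size Calculation). The week-8 means and SDs, and the baseline entries 1 and 4, are assumptions. With a constant baseline entry b,

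t = (m − b) / (SD / √n).

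For SD 1.5 and n = 30, the standard error is 1.5/√30 = 0.274.

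| Week-8 mean m | SD | t if b = 1 | t if b = 4 |
|---|---|---|---|
| 4 | 1.5 | 3/0.274 = 10.95 (p < 0.001) | 0/0.274 = 0 (p = 1) |
| 5 | 1.0 | 21.91 | 5.48 |
| 5 | 1.5 | 14.61 | 3.65 (p = 0.001) |
| 5 | 2.0 | 10.95 | 2.74 (p = 0.010) |

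With 26 patients, mean 5 and SD 1.5, the values are 13.60 and 3.40. In the first row the same ratings give opposite conclusions.

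The signed-rank alternative has the same weakness. If 1, the scale minimum, is entered at baseline, no difference can be negative. With k non-zero differences, all positive, the exact two-sided p is 2/2^k: 0.0625 for k = 5 and 0.031 for k = 6. Six of 30 patients scoring above 1 would then be enough for significance, and worsening could never appear. This needs no assumed mean or SD, but it does need the assumed entry of 1.

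**What is not affected.** If every patient has the same entry b, the between-group difference in mean change is (m₁ − b) − (m₂ − b) = m₁ − m₂. Subtracting a constant leaves SDs, ranks and correlations as they were. The between-group CGI-I test and any correlation using CGI-I therefore do not depend on b.

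**The case against.** The strongest reply is that the defect is inferred. A baseline CGI rating could mean CGI-S alone, and improvement from baseline could describe a week-8 CGI-I rating made with baseline as its reference. A paired test presupposes two measurements, so item 2 might be taken to pass over CGI-I. This stands as far as it goes: a reader might infer that the protocol orders a baseline CGI-I rating, and no sentence does. But the Follow Up section speaks of the scales, in the plural, being rated again, and nothing limits CGI-I to week 8. On the week-8-only reading, the plan still names a test that cannot be run for CGI-I.

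A second reply is that the protocol cites a source for CGI and restates only range and direction for its other scales too. That also stands. A reader might infer that no no-change score exists, but the documents show only that the protocol does not restate one.

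Third, a reader might call the paired test uninterpretable outright, or say that its result reflects the baseline entry instead of patients' response. Neither is supported. With the no-change score entered, the test is valid. Response also moves the result: at SD 1.5 and n = 30, raising the week-8 mean from 4 to 5 takes t from 0 to 3.65 when 4 is entered, and from 10.95 to 14.61 when 1 is entered. Both the entry and the response matter.

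Finally, nothing in the documents suggests that 1, 4 or any other constant would be entered. The t values show how sensitive the test could be; they do not predict this trial's results.

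**Conclusion.** The concern holds as a minor defect in the analysis plan. Read literally, one scheme covers both CGI scales, and it does not fit CGI-I. The within-arm CGI-I test depends partly on a pre-treatment entry that the plan does not define, and is interpretable only if that entry is the no-change score. If CGI-I is rated at week 8 only, the test has no pair.

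The possible swing is large under assumed values (t of 10.95 against 0 for the same ratings), but the reach is narrow: a within-arm test on one part of one secondary outcome. A reader might infer that the CGI comparison between treatments is compromised. With a common baseline entry it is not. Change from baseline in CGI-S is valid, and the primary CDSS analysis is untouched.

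The conclusion about the text needs no assumed number. The illustration rests wholly on the assumed week-8 means, SDs and baseline entries.

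**What to change.** - In secondary objective 1, the Methodology and Follow Up text, secondary outcome 1 and Statistical Analysis Plan items 2 and 3, state that CGI-I is rated at week 8 only, relative to baseline. Compare it directly between groups, for example by Mann-Whitney U, with no baseline rating, change score or paired test.
- State the CGI-I no-change score, so that each arm's week-8 result can be read as improvement or worsening.
- Keep baseline and week-8 ratings and the paired test for CGI-S. Between groups, compare week-8 CGI-S adjusted for baseline CGI-S (ANCOVA). The planned change-score comparison is valid; the adjustment is a gain in precision from data already collected.
- In item 4, name the CGI score to be correlated (CGI-S change or week-8 CGI-I), since the two scales run in opposite directions as described.

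The cost is wording only: no new data, visits or patients.

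### The only safety outcome is the adverse drug reaction, so events are counted after a causality judgement that the stated blinding does not cover

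*Combined protocol and SAP*

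**What the plan says.** Safety is a comparative aim. The Aim reads "To compare the efficacy and safety of low dose Amisulpride Versus Olanzapine-Fluoxetine Combination", and the Follow Up section says the changes will be "compared in-between the groups to find out the efficacy and safety of one treatment over the other".

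The only safety measure is the adverse drug reaction. Secondary objective 4 is "To detect adverse drug reactions (if any) and grading their severity", and secondary outcome 4 under Outcome Measures is "Detect adverse drug reactions (if any) and grading their severity", over 8 weeks. No all-cause adverse event, laboratory measure or repeated extrapyramidal scale is listed as an outcome. The Simpson-Angus Scale appears only among the inclusion criteria.

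On masking, Study Design states "The proposed study will be a randomized, rater-blinded, controlled, clinical trial". The Blinding section gives the scope: "The ratings of the CDSS and CGI scales would be done by a psychiatrist who would be blinded". Adverse drug reactions are not mentioned there, and no masking of patients or treating staff is described. Under Methodology, one arm takes amisulpride alone and the other takes olanzapine plus fluoxetine.

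The 8-week assessment in the Methodology section is "The follow-up assessment would involve a re-evaluation of the CDSS and the CGI scores and the Serum BDNF levels", with no safety item. The SAP names only CDSS, CGI and BDNF as analysis variables.

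**The concern.** An adverse drug reaction is a filtered count: an event enters only after someone has decided that the drug caused it. The outcome in each arm is then the product of two things, how often events occur and how readily they are attributed. A comparison of arms isolates the first only if the second is equal in both.

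The plan gives no assurance of that. The described blinded task stops at two efficacy scales, the assessor of reactions is not named, and no second safety measure is planned that could show whether attribution differed. What is at stake is the safety half of the title and aim. A difference in reactions could reflect attribution alone, and a real difference in events could be masked. The primary CDSS analysis is not affected.

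**Working it through.** **The plan's own figure.** The documents give no figure for the safety comparison. The only calculation is for CDSS: difference 3, known SD 3.8, two-sided 0.05, 80% power. It reproduces: n = 2 × (1.96 + 0.8416)² × 3.8² / 3² = 25.2, so 26 per group (power 81.2% with known SD; a t-based calculation gives 26.2, or 79.7% power at 26). With 13% attrition, 26 / 0.87 = 29.9, so 30. This is used below only to fix the number per arm.

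**Model.** Recorded reaction rate = true event risk × share of events attributed to drug. If the true risk p is the same in both arms and the shares are a and b, the false gap is p × (b − a).

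**Inputs.** 30 per arm, from Sample Size Calculation. True risks of 30%, 50% and 70% and all attribution shares are assumptions; the documents give none. CI half-width = 1.96 × √[r₁(1 − r₁)/30 + r₂(1 − r₂)/30], where r₁ and r₂ are the recorded rates. False-positive rates are exact binomial sums over all possible tables at two-sided 0.05.

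| True risk, both arms | Attributed (arm 1 / arm 2) | Recorded | False gap (points) | 95% CI half-width (points) | False positive, Fisher | False positive, uncorrected chi-square |
|---|---|---|---|---|---|---|
| 30% | 60% / 60% | 18% / 18% | 0 | 19 | 2.1% | 5.0% |
| 50% | 60% / 60% | 30% / 30% | 0 | 23 | 2.6% | 4.9% |
| 70% | 60% / 60% | 42% / 42% | 0 | 25 | 2.6% | 5.0% |
| 30% | 60% / 70% | 18% / 21% | 3 | 20 | 2.7% | 5.9% |
| 50% | 60% / 70% | 30% / 35% | 5 | 24 | 3.9% | 6.7% |
| 70% | 60% / 70% | 42% / 49% | 7 | 25 | 5.0% | 8.6% |
| 30% | 50% / 75% | 15% / 22.5% | 7.5 | 20 | 6.0% | 11.2% |
| 50% | 50% / 75% | 25% / 37.5% | 12.5 | 23 | 11.8% | 17.6% |
| 70% | 50% / 75% | 35% / 52.5% | 17.5 | 25 | 19.8% | 27.9% |

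Allocation is 1:1, so swapping the arms reverses the sign of each gap and leaves its size and false-positive rate unchanged.

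**Masking a real difference.** Again on assumed figures: a true risk of 70% with 50% attributed gives 0.70 × 0.50 = 35%. A true risk of 50% with 70% attributed gives 0.50 × 0.70 = 35%. A 20-point difference in events disappears.

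**What the table shows.** Mild differential attribution (60% / 70%) does little at this sample size: Fisher's test stays at or below 5%. The stronger case (50% / 75%) raises the Fisher rate to 6-20%, against 2-3% with equal attribution. Every gap in the table is smaller than the half-width of its confidence interval.

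**The case against.** The strongest objection is that the documents never say who detects, attributes or grades reactions. A reader might infer that unblinded staff do so, because the regimens look different and only CDSS and CGI are assigned to the blinded psychiatrist. That inference is plausible but not documented: the trial is called rater-blinded without restriction in Study Design, and the blinded rater could also collect reactions. This part of the objection stands. It does not settle the matter, since judging whether a drug caused an event usually calls for knowing which drug was taken. Giving that task to the blinded rater would risk unblinding the person who scores the primary outcome, or leave the attribution uninformed.

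A reader might also infer that any bias favours amisulpride, because Expected Outcome lists "Lesser risk of side-effects in the patients, as Amisulpride is a relatively safer drug among other antipsychotics". That is a recorded expectation, not evidence of direction. The line compares amisulpride with other antipsychotics in general, and the Scientific Background says the drug has not been studied in this condition, which could equally lead staff to attribute more events to it. This part stands too: the direction is unknown.

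It can further be said that the missing assessor, causality method, grading scale and visit timing are mere omissions. They are omissions, but filling them in would leave an outcome that filters events by cause before counting them. Ethical Issues, item 7, which speaks of adverse reactions arising from the interventions, supports reading the term that way.

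Finally, with 30 per arm, sampling error exceeds every tabulated false gap. That is true, and it limits what the trial can say about safety on any definition. It is no reason to add an avoidable source of bias.

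**Conclusion.** The concern holds as a risk in the definition of the safety outcome. Reactions are the sole safety outcome of a trial that sets out to compare safety, and no stated blinding protects the judgement on which they depend. Attribution could differ by arm and create or hide a difference.

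The size is unknown. False gaps of 3-7 points (60% against 70% attributed) and about 8-18 points (50% against 75%) follow only from the assumed shares and assumed true risks of 30-70%, and apply in either direction. The documents do not support saying that the judgement is made by unblinded staff, or that the bias runs in favour of amisulpride. This is a cheap improvement to a secondary outcome; it does not threaten the primary analysis.

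**What to change.** In secondary objective 4 and secondary outcome 4, make the safety outcome all treatment-emergent adverse events, whatever the judged causality, elicited with the same checklist at the same time points in both arms. State who elicits them and whether that person knows the arm.

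Add to the SAP, for each arm, the number and percentage of patients with at least one event, and the risk difference between arms with its 95% CI. Keep causality-judged reactions and severity grades as a secondary listing.

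The cost is an event checklist, a short SAP addition and more minor events to record for 60 patients. The follow-up sections currently list no safety item, so the checklist and its time points must be added there as well. The change removes the dependence on causality attribution. It reduces, but does not remove, bias from patients who know their treatment reporting differently, or from staff who know the arm asking differently.

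### No eligibility criterion addresses pregnancy or breast-feeding, so as written such women are eligible and could be randomised

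*Combined protocol and SAP*

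**What the plan says.** INCLUSION CRITERIA opens with "All patients coming for treatment at the OPD and IPD of the Department of Psychiatry fulfilling the following are included". Six items follow: the ICD-10 diagnosis, age and sex ("Aged between 18 to 60 years of either sex"), three rating-scale limits, and consent from the legally authorised relative.

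EXCLUSION CRITERIA opens with "Patients with any one of the following are excluded from the study" and has five items. The first is "Patients with a medical or neurological disorder" and the last is "Patients already on Olanzapine-Fluoxetine combination or Amisulpride". Between them stand past substance dependence, high suicidality and earlier primary depression.

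RANDOMIZATION states: "All recruited patients will be randomized by computer-generated random number into two treatment groups with an allocation ratio of 1:1". METHODOLOGY continues, after randomisation and the collection of sociodemographic and clinical data: "Then at baseline, the CDSS and CGI ratings would be assessed, and the serum BDNF would be tested for each patient". On follow-up it says: "The two groups would be followed for 8 weeks, at the completion of which all the patients would be reassessed".

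OUTCOME MEASURES lists adverse drug reactions as a secondary outcome with an 8-week time frame and gives no assessment times. ETHICAL ISSUES, item 6, says in general terms that the efficacy and safety of the medications used are already established.

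**The concern.** The inclusion list takes in women of child-bearing age, and the exclusion list says nothing about pregnancy or breast-feeding. A recruiter who follows both lists to the letter has no ground for turning away a pregnant or breast-feeding woman. She could then be assigned by chance to amisulpride or to olanzapine with fluoxetine for 8 weeks.

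What is at stake is the protection of the woman and of a fetus or infant, in a trial that names safety in its AIM. There is also a matter of consistency. One recruiter might stretch the item on medical disorders to cover pregnancy and another might not, so that entry would depend on who screens.

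**Working it through.** The point rests on reading the lists against each other. The only arithmetic is a check that the planned sample size does not depend on it.

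**Eligibility text**

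1. Do the inclusion items admit these women? Yes. Item 2 sets age and sex only. The diagnosis, the scale limits and the consent item do not refer to pregnancy, lactation or contraception.
2. Does an exclusion remove them? Four of the five items concern substance dependence, suicidality, past depression and current study drugs, and are not relevant. The remaining item covers disorders, and on a plain reading neither pregnancy nor breast-feeding is a disorder.
3. Does another section supply the rule? METHODOLOGY, RANDOMIZATION, FOLLOW UP, OUTCOME MEASURES and ETHICAL ISSUES mention neither state, and no pregnancy test is listed.
4. Would a later step detect it? The procedures named at baseline are CDSS, CGI and serum BDNF, and METHODOLOGY places them after randomisation. The same three are named for the reassessment at 8 weeks. No visit is listed between the two.

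The two lists, followed exactly, therefore leave pregnant and breast-feeding women eligible.

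**Sample size**

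Inputs from SAMPLE SIZE CALCULATION: difference 3, SD 3.8, two-sided significance level 0.05, power 80%, attrition 10-15%, with 26 per group needed and 30 per group recruited.

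- By the normal approximation, n per group = 2 × (1.960 + 0.842)² × 3.8² / 3² = 2 × 7.85 × 14.44 / 9 = 25.2, rounded up to 26. This reproduces the plan's figure.
- Power at 26 per group is 81.2% by the normal approximation and 79.7% by the noncentral t distribution, both close to the stated 80%.
- Allowing for attrition, 26 / 0.90 = 28.9, or 29. 26 / 0.87 = 29.9, or 30. 26 / 0.85 = 30.6, or 31. The stated 30 lies within this range.

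No term in these formulas refers to the excluded groups. Women excluded at screening are never randomised, so they do not count as attrition. If k otherwise eligible women are excluded, the site must find 60 + k candidates to randomise 60. The documents give no value for k.

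**The case against.** **The protocol has other safeguards.** Written consent from the legally authorised relative is needed after risks and benefits are explained, and the ethics committee must approve the study before it starts. This stands in part: a woman who meets the criteria is eligible and could be randomised, but it does not follow that she would be. Consent is not an eligibility rule, however, and it does not alter the two lists.

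**The rule may be written elsewhere.** The consent form and the data-collection sheets were not available to check and may mention pregnancy. That limit is real. Wording there would still not amend the eligibility list.

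**The drugs' safety is said to be established.** ETHICAL ISSUES, item 6, makes that statement in general terms. It does not mention pregnancy or breast-feeding, so it does not show that the protocol considered them.

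**No harm is documented.** This is correct. A reader might infer that the documents show either regimen to be hazardous in pregnancy or lactation, but they do not. The remark in SCIENTIFIC BACKGROUND that amisulpride is unexplored concerns post-schizophrenic depression and says nothing about fetal risk. The point is that the entry rule is silent.

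**Patients are followed throughout.** A reader might infer that patients have no scheduled contact with the trial once treated. The documents do not support that. They describe 8 weeks of follow-up and a reassessment of all patients at its end, and they include in-patients. The supportable statement is that no visit is listed between baseline and week 8.

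**Conclusion.** The point holds as an omission from a stated rule: as written, pregnant and breast-feeding women are eligible and could be randomised. It should be corrected, because following the lists exactly gives a worse result for patient safety and the remedy is small.

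No number of affected women can be given. A reader might try to size the problem by assuming a share of women among the 60 patients. That would count every woman aged 18 to 60, including those past child-bearing age, and would not estimate how many are pregnant or breast-feeding. The documents give no sex mix, age mix or pregnancy rate, and the number could be zero.

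The primary comparison and the analysis methods are unaffected. The sample size of 26 evaluable and 30 recruited per group is also unaffected, on the assumption that the SD of 3.8 still applies once a few women are excluded. The verdict further assumes that the exclusion on medical disorders is read in its ordinary sense.

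**What to change.** - Add pregnancy and breast-feeding to EXCLUSION CRITERIA, subject to agreement by the sponsor and the ethics committee.
- Confirm both by history at screening, with the answer recorded before randomisation. METHODOLOGY already selects patients against the criteria before it randomises them, so the question fits the existing sequence.
- Record any pregnancy reported by week 8 with the safety data.

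The baseline BDNF blood sample should not be counted on for a pregnancy check at entry. METHODOLOGY places it after randomisation, so a result from it would come too late to decide eligibility.

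The cost is one eligibility line, one screening question and one item in the safety record. A few otherwise eligible women would not be enrolled, and the site would have to screen that many more candidates. The target of 30 per group stays as planned.
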